5.3. Toxicity Criteria

This study will utilize the CTCAE version 3.0 for toxicity and adverse event reporting. A copy of the CTCAE version 3.0 can be downloaded from the CTEP home page (<http://ctep.info.nih.gov>). All appropriate treatment areas should have access to a copy of the CTCAE version 3.0.

5.4. Statistical Section

The primary objective of the trial is to determine if there is a difference in overall survival among patients with limited gastric cancer metastases who are randomized to receive either systemic therapy alone or gastrectomy, metastasectomy and systemic therapy.

Based upon results in the literature, patients who would be eligible for this trial and who receive systemic therapy alone would be expected to have an estimated 12-month median overall survival from the date of randomization. The goal of this study will be to determine if the use of gastrectomy, metastasectomy and systemic therapy will result in an 8-month increase in overall survival, to a median of 20 months. Patients will be randomized between systemic therapy alone or gastrectomy, metastasectomy and systemic therapy and followed for overall survival. Kaplan-Meier curves and a two-tailed log-rank test will be the primary analysis methods. Assuming exponential overall survival curves, the hazard rate for the systemic therapy is 0.0578, or approximately a 5.8% probability of death each month when the median survival is 12 months. If we assume that the surgery plus systemic therapy arm has a median overall survival of 20 months, this corresponds to a hazard rate of 0.0347, and the resulting hazard ratio for the comparison of the two overall survival curves would be 1.67. To compare these curves and detect a difference with a 0.05 two-tailed log-rank test, a total of 68 evaluable subjects per arm (136 total) will need to be enrolled over a 6-year period and followed for an additional 2 years from the date of entry of the last patient, with 121 total deaths, in order to have 80% power to compare the curves.

Patients will be stratified for site of metastases (liver, peritoneal, or lung), disease-free survival and prior systemic therapy for gastric metastases.

Progression-free survival will also be evaluated using Kaplan-Meier curves, and a two-tailed log rank test, as a secondary endpoint. In addition, a prognostic factor evaluation using Cox proportional hazards modeling will take place after the study has concluded in order to identify if there are factors which can be identified that are associated with survival or progression free survival in patients randomized to treatments on this trial; this will also be interpreted as a secondary endpoint.

The study will be monitored by the NCI/CCR Data Safety and Monitoring Board on an annual basis to evaluate the safety of the two arms. The SAEs (typically grade 3 toxicities, or greater) will be reported according to type of toxicity, and maximal grade noted per patient, for toxicities with at least a possible attribution to the therapy provided on that arm. Comparisons will be made between the two arms using Cochran-Armitage tests for trend, or other appropriate methods, to determine if there is increased toxicity associated with either arm.

In addition, at the first Data Safety and Monitoring Board (DSMB) meeting held following the point at which half of the required total subjects have been enrolled (68 total), a single evaluation for futility will be undertaken. Evaluations for better than expected efficacy will also be made annually, beginning after half the subjects have been enrolled.

The futility evaluation will be performed as follows: based on the full data available at the time, a conditional power analysis will be performed to determine if the trial is unlikely to find an effect at the 0.05 two-tailed significance level with continued accrual based on an overall survival endpoint. Median survivals of 12 and 20 months correspond to 12-month survivals of 50% and 66% respectively. Using these as the values under the alternative, and using the actual proportions alive at 12 months, based on the observed fractions and the expected sample sizes at 12 months, the conditional power of the trial will be determined assuming accrual of the remaining patients to achieve a total of 136 patients. If the conditional probability of finding a difference at the two-sided 0.05 level at the conclusion of the trial is less than 20%, then it will be reasonable to recommend that no further patients will be enrolled.

The evaluation for better than expected efficacy will be performed as follows. Beginning at the first annual DSMB meeting after 68 patients have been randomized, annual interim evaluations will be performed to determine if there is sufficient evidence to terminate accrual because of a better than expected improvement in overall survival. An alpha spending function approach to monitoring will take place using an O'Brien-Fleming interim evaluation boundary ⁷⁹. It will be assumed that a total of 121 deaths would take place over a total of 8 years of accrual plus monitoring, and that monitoring would begin after approximately 40-45 deaths have been noted. The information fraction used to compute the interim boundary at each annual evaluation will be calculated as the number of patients who died /121.

Quality of life evaluations will be compared between the two study arms, with comparisons at multiple individual time points, as well as with respect to changes from baseline. Wilcoxon rank sum tests will likely be used. The evaluation will be considered secondary, and p-values resulting from the analysis will be presented without adjustment for multiple comparisons, but in the context of the number of tests evaluated.

It is expected that 24 patients per year can be accrued onto this trial, and thus accrual will be completed in approximately 6 years. Allowing for a very small number of inevaluable patients, the accrual ceiling will be set at 140 patients.

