Abbreviated Title: Metastatic Gastric Cancer

CC Protocol Number: 09-C-0189 G

Prospective Randomized Trial Comparing Gastrectomy, Metastasectomy plus Systemic Therapy versus Systemic Therapy Alone: GYMSSA Trial

Principal Investigator: [name]., PhD¹

Lead Associate Investigator: [name].¹

Associate Investigators: [name].¹
[name].¹
[name].¹
[name].²
[name], PharmD⁴
[name].³
[name].⁵
[name], R.N.¹
[name], R.N.¹
[name], R.N.¹
[name].⁶

¹Surgery Branch, CCR, NCI

²Medical Oncology Branch, CCR, NCI

³Laboratory of Pathology, CCR, NCI

⁴NIH Clinical Center Pharmacy

⁵Diagnostic Radiology Department, NIH Clinical Center

⁶Biostatistics and Data Management Section, CCR, NCI

Version Date: May 17, 2012

Date of Submission: May 29, 2009

PRECIS

Background:

- The standard of care for metastatic gastric cancer (MGC) is systemic therapy resulting in median survival of 6-12 months and rare survivors of up to three years.
- For patients with limited MGC, retrospective studies have shown improved overall survival following gastrectomy and/or metastasectomy plus systemic therapy (e.g. median survival after liver resection for metastatic gastric cancer of 15-37 months, with a five year survival rate of 25%).
- This prospective randomized trial for patients with MGC and limited metastases is designed to compare two therapeutic approaches: gastrectomy with metastasectomy plus systemic therapy (GYMS) vs. systemic therapy alone (SA) and to evaluate outcome in light of selection criteria to define those patients who may benefit from the more aggressive approach.

Objectives:

Primary Objective:

- To compare two therapeutic approaches: GYMS vs. SA in terms of overall survival in patients with limited MGC.

Secondary Objectives:

- To analyze selection criteria for patients who might benefit from the GYMS approach.
- To determine progression-free survival in both arms.

Eligibility:

- MGC with limited metastatic disease thought to be resectable to no evidence of disease.
- 18 years old or greater with an ECOG 0-2
- Laboratory and physical examination parameters within acceptable limits by standard of practice guidelines prior to surgery

Design:

- Patients will be randomized to receive gastrectomy and metastasectomy followed by systemic chemotherapy (GYMS) or systemic chemotherapy (SA) alone and will be stratified based on sites of metastatic disease, previous therapy and disease free interval (Appendix 3, trial schema).

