- Patients in both arms will receive the FOLFOXIRI regimen (5-FU, leucovorin, oxaliplatin and irinotecan)
- No cross over will be allowed.
- Survival analysis will be done in intention to treat fashion from time of randomization.
- Based on estimated 12 and 20 months overall survival for the SA and the GYMS arms respectively, 68 patients per arm (power=0.80, 0.05 two-tailed log-rank test) will be enrolled. Patients will be recruited over 6 years and followed for an additional 2 years from the date of entry of the last patient.

Table of Contents

1. Introduction:	4
1.1. Study Objectives	4
1.2. Background and Rationale	4
2. Eligibility Assessment and Enrollment:	10
2.1. Eligibility Criteria	10
2.2. Research Eligibility Evaluation	12
2.3. Patient Registration, Stratification, and Randomization	14
3. Study Implementation:	15
3.1. Staging Laparoscopy	16
3.2. Gastrectomy, Metastasectomy, Peritonectomy and Intraperitoneal Therapy	16
3.3. Intraperitoneal Chemotherapy CHPP	20
3.4. Postoperative Care	21
3.5. Systemic Chemotherapy Therapy	22
3.6. Treatment Evaluation During Chemotherapy:	24
3.7. Evaluation of Response and QOL Assessment	24
3.8. Off Treatment Criteria	25
3.9. Post Treatment Follow up (Both Arms)	25
3.10. Off Study Criteria	25
3.11. Measurement of Health Related Quality of Life	26
4. Supportive Care:	27
5. Data Collection and Evaluation:	28
5.1. Data Collection	28
5.2. Response Criteria	28
5.3. Toxicity Criteria	29
5.4. Statistical Section	30
5.5. Safety and Monitoring Plan	31
5.6. Clinical Trial Monitoring Plan	32
6. Human Subject Protection:	32
6.1. Rational for Subject Selection	32
6.2. Evaluation of Potential Benefits and Risks	33
6.3. Risks/Benefit Analysis	33
6.4. Consent Process	33
7. Data Reporting:	34
7.1. DEFINITIONS	34
7.2. Routine Data Reporting	35
7.3. Exclusions to Routine Data Reporting:	36
7.4. NCI-IRB REPORTING	37
8. Pharmaceutical Information:	37
8.1. Oxaliplatin	37
8.2. Leucovorin Calcium (Injection)	38
8.3. 5-Fluorouracil	39
8.4. Irinotecan	40
9. References:	42
10. Figures, Tables and Appendices	48

1. Introduction:

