2.1. Eligibility Criteria

2.1.1. Inclusion Criteria

- a. Histologically or cytologically confirmed gastric adenocarcinoma
 - b. Metastatic disease must be measurable by CT and/or MRI
 - or*
 - There must be a history of positive peritoneal washings or carcinomatosis
 - c. All disease should be deemed resectable to negative margins (NED) based on imaging studies e.g.:
 - Esophageal invasion <4cm that does not require thoracotomy (Seiwert II and III lesions)
 - Hepatic metastases (unilateral or bilateral ≤ 5 lesions, ≤ 15 cm total diameter)
 - Primary peritoneal metastases (small disease load \leq P2 disease) without massive ascites or intestinal obstruction
 - Para-aortic lymph node metastases (stations 16 a1 and/or b2, see appendix 5)
 - Lung metastases (≤ 3 unilateral/bilateral, 9 cm total diameter)
 - Patients who present with both hepatic and peritoneal metastases must have no evidence of extensive para-aortic/retro-pancreatic lymph node metastases
- Note:** Patients with both pulmonary and peritoneal metastases will be enrolled at the discretion of the PI
- d. Greater than or equal to 18 years of age
 - e. Must be able to understand and sign the Informed Consent Document
 - f. Clinical performance status of ECOG ≤ 2
 - g. Life expectancy of greater than three months
 - h. Patients of both genders must be willing to practice birth control during and for four months after receiving chemotherapy
 - i. Hematology:
 - Absolute neutrophil count greater than $1500/\text{mm}^3$ without the support of Filgrastim.
 - Platelet count greater than $75,000/\text{mm}^3$.
 - Hemoglobin greater than 8.0 g/dl.
 - j. Chemistry:
 - Serum ALT/AST less or equal to 5 times the upper limit of normal; except in the presence of obstructive liver metastases where ALT/AST may be up to 10 times the upper limit of normal
 - Serum creatinine less than or equal to 1.5 mg/dl unless the measured creatinine clearance is greater than $60 \text{ mL/min}/1.73 \text{ m}^2$
 - Total bilirubin less than or equal to 2 mg/dl, except in the presence of obstructive metastases
 - PT within 2 seconds of the upper limit of normal (INR ≤ 1.8)
 - k. No history of prior/other malignancies within the 2 years prior to enrollment with the exception of basal cell carcinoma

2.1.2.

Exclusion Criteria

- a. Prior treatment with FOLFOXIRI (treatment with any of the components as separate regimens is allowable)

- b. Inability to tolerate any of the chemotherapeutic agents

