2.3. Patient Registration, Stratification, and Randomization

Registration of patients onto this study will take place within 10 days of the patient signing the consent by faxing a completed eligibility checklist to the Central Registration Office (CRO) at [contact] between 9:00 and 5:00 Monday through Friday. Following laparoscopy, patients will be stratified and then randomized by the CRO to receive gastrectomy and/or metastasectomy plus systemic therapy (GYMS arm) or standard therapy (SA arm). The CRO will notify the Study Coordinator of the results of randomization.

Note: As soon as the patient has signed the informed consent, the patient's referring oncologist (or [name] or his designee for those patients being treated at the NCI) will be notified of the expected date of randomization and potential start dates for the chemotherapy. Immediately following randomization the referring oncologist will be notified. Subjects who are randomized to receive chemotherapy only must begin chemotherapy treatment within 14 days following randomization.

Stratification will be done according to the following factors:

- Site of metastases (liver, lung, and peritoneal disease). Note: positive peritoneal washings will be stratified as peritoneal disease.
- Time to development of first metastases (earlier than 1 year vs. later than 1 year)
- Previous systemic therapy specifically given for gastric metastases vs. no therapy for metastatic disease. (**Note:** patients who have received adjuvant chemotherapy will be stratified to the *no therapy for metastatic disease* group)

3. Study Implementation:

Study Design (See appendix 3 for trial schema)

Experimental Design:

- This is a prospective randomized trial comparing the effects of two therapeutic approaches, gastrectomy and/or metastasectomy plus systemic therapy (GYMS) to systemic therapy alone (SA) on the overall survival of patients with limited gastric cancer metastases.
- Patients who are newly diagnosed as well as those who have received prior systemic treatment for gastric metastases will be eligible. Both groups will be randomized to surgery plus chemotherapy or chemotherapy alone.
- Candidate patients for this trial will undergo all or part of the following staging elements before randomization and/or if indicated medically: pathologic confirmation of gastric cancer as feasible, H&P, laboratory evaluations, imaging studies and other studies as medically indicated.

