- Patients who enroll and are willing to have tissue collected for research purposes will be enrolled on protocol 09-C-0079.
- All patients found eligible will undergo staging laparoscopy with peritoneal lavage prior to randomization.
- Patients will be randomized following staging laparoscopy and after the results of the peritoneal washings are available.
- Stratification will adjust for site of metastases (liver, peritoneal and lung), disease-free interval (DFI), and previous systemic therapy for gastric metastases. Note: positive peritoneal washings will be stratified as peritoneal disease.
- Patients randomized to the GYMS approach and who have peritoneal disease will undergo, as an integral part of their treatment, complete peritonectomy and peritoneal perfusion (CHPP).
- Patients who present with intrabdominal disease without peritoneal involvement will undergo CHPP with limited peritonectomy as described in section 3.2.6
- All patients randomized to the GYMS arm will undergo gastrectomy, modified D2 lymph node dissection and/or appropriate metastasectomy followed by systemic therapy.
- *H. pylori* infection will be tested and treated following the recommendations of the American College of Gastroenterology guideline on the management of *H. pylori* infection⁷⁵ (Appendix 2). This treatment should not delay surgery.
- Patients randomized to the systemic therapy arm (SA) will receive systemic therapy preferably by their home medical oncologist or by the NCI Medical Oncology Branch.
- Systemic therapy: Since there is no definitive standard of care in metastatic gastric cancer and oxaliplatin and/or irinotecan were shown in phase III trials⁷⁶ to be equally effective to other common regimens in gastric cancer, patients will receive the FOLFOXIRI regimen as described by Masi et al from the GONO group⁷⁷.
- Patients in the SA arm who develop metastases synchronous to the primary gastric cancer will be eligible for palliative gastrectomy for pain, bleeding, obstruction and/or if deemed in the best interests of the patients.
- Palliative gastrectomy will include tumor resection (R0 when possible) and a bypass. As per standard of care, no adjacent organ resection (with the exception of obstructing lesions) will be performed.

- During follow up, all patients will undergo H&P laboratory evaluation and imaging studies and tumor markers as indicated. The timing of all follow up evaluations will be based on the date of randomization.

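### Randomisation is stratified by three factors but the primary log-rank is not said to use them: the test is valid, and adjusting for the factors is an optional, cheap gain if they predict survival

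*Combined protocol and SAP*

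**What the plan says.** Section 5.4 names the primary analysis: "Kaplan-Meier curves and a two-tailed log-rank test will be the primary analysis methods". The Precis sizes the trial on the same test: "68 patients per arm (power=0.80, 0.05 two-tailed log-rank test) will be enrolled". Neither place says stratified or adjusted.

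Section 5.4 then lists the factors: "Patients will be stratified for site of metastases (liver, peritoneal, or lung), disease-free survival and prior systemic therapy for gastric metastases". Section 2.3 gives the levels. Site is liver, lung or peritoneal, with positive washings counted as peritoneal. Prior systemic therapy for metastases is yes or no. The time factor is "Time to development of first metastases (earlier than 1 year vs. later than 1 year". The design list in Section 3 has "Stratification will adjust for site of metastases (liver, peritoneal and lung), disease-free interval (DFI), and previous systemic therapy for gastric metastases". That line stands among the allocation steps and describes the randomisation, not the test. The Precis has patients "stratified based on sites of metastatic disease, previous therapy and disease free interval (Appendix 3, trial schema".

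The only covariate model is a Cox prognostic-factor evaluation in Section 5.4, run after the study and treated as secondary. The interim efficacy rule in the same section gives an O'Brien-Fleming boundary and an information fraction of deaths over 121. It does not name the interim statistic, although the log-rank is implied.

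On site, Section 2.1.1 admits patients with more than one site ("Patients with both pulmonary and peritoneal metastases will be enrolled at the discretion of the PI"; "Patients who present with both hepatic and peritoneal metastases must have no evidence of extensive para-aortic/retro-pancreatic lymph node metastases"). Sections 2.1.1 and 3.2.7 also allow para-aortic nodal disease, which can be the only metastatic site.

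**The concern.** Stratified randomisation balances the arms on the factors, which removes their contribution to chance differences between arms. A plain log-rank still counts that contribution in its variance. If the factors predict survival, the test statistic varies less than the test assumes, so the test becomes conservative. If the treatment effect is 1.67 within strata, mixing strata also pulls the overall hazard ratio towards 1. Both effects cost power, and the factors are already recorded at randomisation.

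The silence matters in a second way. One analyst could run a plain log-rank and another a log-rank over every stratum, and both could claim to follow the plan. In a trial of 136 patients these are not equivalent.

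**Working it through.** **1. The plan's own figures.** Inputs from Section 5.4: medians 12 and 20 months, two-sided 0.05, 80% power, 68 per arm, 72 months' accrual plus 24 months' follow-up.
- Hazards: ln 2/12 = 0.0578 and ln 2/20 = 0.0347; ratio 1.667.
- Schoenfeld: d = 4(1.960 + 0.842)²/(ln 1.667)² = 4 × 7.849/0.2609 = 120.3, so 121.
- Power at 121 deaths: Φ(√121/2 × 0.5108 − 1.960) = Φ(0.850) = 80.2%.
- P(death) = 1 − [exp(−24λ) − exp(−96λ)]/(72λ) = 0.941 and 0.840; 68 × (0.941 + 0.840) = 121.1 expected deaths.

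Both figures reproduce.

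**2. Simulation set-up.** The documents give no prognostic hazard ratios, factor prevalences or block size, so these are assumed. Allocation is in permuted blocks of 4 within strata. Patient mixes:
- A: liver/peritoneal/lung 60/30/10%, 70% with the interval under 1 year, 30% pretreated.
- B: 40/50/10%, 50%, 50%.
- C: 55/40/5%, 70%, 30%.

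The adjusted test uses a Cox model with the three factors as main effects. It is held at 5% by a calibrated cut-off (A, B) or a re-randomisation p-value (C). Each setting has 20,000 trials, except 10,000 for power in A and B. Calendar time is fixed, so deaths drift down (in A, to 119.2 at prognostic HR 1.5 and 115.8 at 2.0).

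**3. Treatment HR 1.67 within strata.** Power is plain log-rank at 1.96 → adjusted test.

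| Prognostic HR, all three factors | Type I error of plain test, A / B / C | Power, A | Power, B | Power, C |
|---|---|---|---|---|
| 1.0 | 5.3 / 5.6 / 5.4% | 80.1 → 77.9 | 79.3 → 77.6 | 79.6 → 77.7 |
| 1.25 (A, B), 1.3 (C) | 4.9 / 4.8 / 4.7% | 77.8 → 77.9 | 77.9 → 77.8 | 77.1 → 77.5 |
| 1.5 | 4.5 / 4.0 / 4.2% | 73.3 → 77.0 | 73.7 → 78.4 | 74.2 → 76.7 |
| 2.0 | 3.2 / 2.9 / 3.1% | 64.4 → 76.1 | 63.2 → 76.2 | 64.4 → 75.6 |

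Part of the gain is recovered conservatism. In mix A at 2.0, a plain log-rank recalibrated to run at exactly 5% has 71.1% power, so 71.1 − 64.4 = 6.7 of the 11.7 points come from that. Part of the loss at 1.0 likewise reflects the plain test running slightly above 5%.

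**4. Treatment HR 1.67 for the overall curves (mix C, exponential arms).** At prognostic HR 1.0/1.3/1.5/2.0, plain power is 79.6/80.5/80.8/81.9% and adjusted power 78.0/80.8/83.1/89.6%. The changes, taken before rounding, are −1.6/+0.3/+2.4/+7.7 points.

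**5. One prognostic factor only.**
- At 1.5: −0.6 to +0.3 points in mix C, and none in mix A (time factor, 77.9 → 77.9).
- At 2.0: +2.1 to +3.5 in mix C, and +3.7 in mix A (time 73.8 → 77.5; site 73.0 → 76.7).

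**6. Log-rank over all cells.** There are 3 × 2 × 2 = 12 cells, about 11 patients each. With 5% lung, 6.8 patients share four cells. Power with no prognostic effect is 73.8% (A), 72.0% (B) and 74% (C), a loss of 6.3, 7.3 and 5.6 points. In mix A this test is still 1.7 points behind the plain log-rank at 1.5 (71.6 against 73.3).

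**7. Error of the adjusted test.** The Cox Wald test at 1.96 runs at 5.1 to 6.0%. The re-randomisation version runs at 4.7 to 5.2%. With five assumed looks (43/64/84/103/121 deaths) and one statistic throughout, overall error at prognostic HR 1.0/1.5/2.0 is 4.7/4.7/4.9% for the re-randomisation z, 5.5/5.4/5.5% for Wald and 5.2/4.2/3.1% for the plain log-rank. Wald at interim looks followed by re-randomisation at the end was not checked.

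**The case against.** The strongest reply is that nothing here is wrong. The planned test controls its error and the power calculation is right. Section 5.4 applies 1.67 to the two overall survival curves, and in that framing the plain log-rank keeps about 80% at every prognostic strength tried. The documents also cannot show that adjustment would pay. Section 1.2 draws on retrospective liver-resection series and gives no hazard ratios. It reports disease-free interval and synchronous presentation as significant in some studies, yet 17 of 29 long-term survivors had synchronous disease. All of this stands, and it makes the point optional.

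It is also fair that the gains were computed under proportional treatment hazards. An early departure caused by surgery was not tested. What the reply leaves open is the silence on whether the strata enter the test, which one sentence would settle.

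A reader might infer more than the documents support:
- That a plain log-rank after stratified randomisation inflates type I error. It becomes conservative as the factors gain strength. The small excess with no prognostic effect (5.3 to 5.6%) does not come from ignoring the factors.
- That the trial is underpowered. The fall to 74% or 64% appears only if 1.67 is applied within strata.
- That stratified randomisation calls for a log-rank over all strata. Here that loses power unless the factors are strong.
- That the site factor has no rule for node-only or two-site patients. The text gives none, but the schema in Appendix 3 is not shown and may do so.
- That the time factor is defined in three conflicting ways. Section 2.3 defines it, and disease-free interval is a natural label for it. Only disease-free survival in Section 5.4 is loose wording.

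**Conclusion.** This is an optional, cheap improvement and not an error. If all three factors have prognostic hazard ratio 1.5 or 2.0, the plain test's type I error is about 4 to 4.5% or 3%. An adjusted test held at 5% then gains about 2 to 4 or 11 to 12 points with 1.67 within strata (4.7 and 13.0 in mix B). With 1.67 for the overall curves the gains are about 2 and 8. There is essentially no gain at about 1.3 or with a single factor at 1.5, and up to about 2 points are lost if no factor matters. These sizes rest on the assumed mixes, block size, prognostic strengths and proportional hazards. The direction is firm, but the size in this trial is unknown.

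**What to change.** Before outcomes are seen, amend Section 5.4 as follows.
- State that the primary treatment comparison is adjusted for the three randomisation factors as main effects in a Cox model, not by a log-rank over all 12 cells. Keep the plain log-rank and Kaplan-Meier curves as supportive.
- Hold the test at 5%, for example with a re-randomisation p-value under the allocation scheme actually used.
- Name one adjusted statistic for the interim and final looks, and check its sequential error under that scheme.
- Use the Section 2.3 definition of the time factor throughout.
- Confirm the site category for node-only and two-site patients, if the schema does not give it.

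No new data, patients or visits are needed. The costs are the possible loss of about 2 power points, a hazard ratio that is conditional on the factors, the need for the registration office's allocation scheme, and the programming and sequential check. If the sponsor prefers the plain log-rank, saying so for both interim and final looks would settle the ambiguity at no cost.
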